11.5 Data Protection and Confidentiality	
11.6 Study Report and Publications	
11.7 Study Files and Retention of Records	
11.8 Case Report Forms	
11.9 Drug Accountability	
11.10 Inspections	
11.11 Access to Information for Monitoring	
11.12 Study Discontinuation	
REFERENCES	

Basic Information

STUDY TITLE: A Phase II, Open Label, Dose Escalation Study of Bermekimab (MABp1) in Patients with Moderate to Severe Atopic Dermatitis

INVESTIGATIONAL PRODUCT:	Bermekimab (MABp1)
IND NUMBER:	112,459
PROTOCOL NUMBER:	2018-PT044
PROTOCOL VERSION / DATE:	3.0/ 22 August 2018
SPONSOR:	XBiotech USA, Inc. [name] U.S.A. [contact]
SPONSOR'S MEDICAL OFFICER:	[name] M.D., MBA XBiotech USA, Inc. [name] U.S.A. [contact]
STUDY CHAIR	[name] [name]

Investigator/Sponsor Signatures

STUDY TITLE: A Phase II, Open Label, Dose Escalation Study of Bermekimab (MABp1) in Patients with Moderate to Severe Atopic Dermatitis

STUDY PRINCIPAL INVESTIGATOR SIGNATURE:

I have read the protocol and appendices. I understand the contents and intend to comply fully with all requirements and the applicable current local and international regulations and guidelines. No changes will be made without formal authorization by XBiotech USA, Inc., in the form of a protocol amendment.

INVESTIGATOR SIGNATURE:

Printed name of Investigator

Signature

Date

SPONSOR SIGNATURE: XBiotech USA, Inc.

[name] M.D., MBA, Medical Director

Signature

Date

Clinical Protocol Synopsis

Study Title: A Phase II, Open Label, Dose Escalation Study of Bermekimab (MABp1) in Patients with Moderate to Severe Atopic Dermatitis
Sponsor:
XBiotech USA, Inc.
Study Chair:
[name] M.D
Sample Size:
29 Subjects

Approximate Duration: The study duration of subject participation is approximately 10 weeks, including a 2 week screening period, a 7 week treatment period, and 1 week follow up period.

Study Objectives:

Primary Endpoint(s):

• Safety and Tolerability

Secondary Endpoints:

- Change in Eczema Area and Severity Index Score (EASI) from baseline to visit 8
- Assessment of Pharmacokinetics (PK)
- Patients (%) achieving Investigator's Global Assessment (IGA) Response (0 or 1) at visit
 8
- Patients (%) achieving ≥2 IGA Score Reduction at visit 8
- Change (%) for peak weekly averaged pruritus and pain numerical rating scores (NRS) from baseline to visit 8
- Change in weekly averaged peak NRS from baseline to visit 8

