- Change in SCORing Atopic Dermatitis (SCORAD) score from baseline to visit 8
- Patients (%) achieving 50% or greater reduction in EASI Score from baseline at visit 8
- Patients (%) achieving 50% or greater reduction in SCORAD Score at visit 8
- Change (%) in Patient Oriented Eczema Measure (POEM) Scores from baseline to visit 8
- Changes in Global Individual Signs Score (GISS) from baseline to visit 8
- Change from baseline to visit 8 in Dermatology Life Quality Index (DLQI)
- Change from baseline to visit 8 in Hospital Anxiety Depression Scale (HADS)

• Change (%) from pre- and post- injection of Visit 1 Questionnaire for pruritus, pain and erythema

Trial Design:

Phase 2, Open label, Dose Escalation Study of Bermekimab (MABp1) in Patients with Moderate to Severe Atopic Dermatitis.

Group A (n=9): patients will receive a total of 4 X 200mg subcutaneous injections of bermekimab. Dosing will occur weekly from visit 1 to visit 4.

Group B (n=20): patients will receive a total of 8 X 400mg subcutaneous injections of bermekimab. Dosing will occur weekly from visit 1 to visit 8.

Inclusion Criteria: No waivers/exemptions will be granted for protocol inclusion/exclusion criteria.

Subjects are included in the study if they meet all of the following criteria:

- Written informed consent provided by the patient
- Age ≥ 18 years
- Chronic Atopic Dermatitis present for at least 3 years
- Disease is not responsive to topical medications, or for whom topical treatments are not indicated or desired
- Willing and able to comply with all clinic visits and study-related procedure
- EASI score ≥ 16 at screening and baseline visits
- IGA score \geq 3 at screening and baseline visits
- $\geq 10\%$ body surface area (BSA) of AD involvement at screening and baseline visits
- Documented recent history (within 6 months before the screening visit) of inadequate response to treatment with topical medications or for whom topical treatments are otherwise medically inadvisable or undesired

Exclusion Criteria:

Subjects with ANY of the following will be excluded from the study:

- Treatment with an investigational drug within 8 weeks of baseline visit
- Having received the following treatments within 4 weeks before the baseline visit, or any condition that, in the opinion of the investigator, is likely to require such treatment(s) during the first 4 weeks of study treatment:

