2.9 CONCOMITANT MEDICATIONS AND PROCEDURES

Any treatment (including nutritional supplements) or procedure administered from the time of consent to the end-of-study visit (visit 9) is considered concomitant and will be recorded in the case report form (CRF). This includes permitted medications ongoing at the time of consent and throughout the study. Concomitant procedures are allowed with the exception of those listed in section 2.9.1.

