3. STUDY DESIGN AND OBJECTIVES

Phase 2, open label, dose escalation study of two dose cohorts of bermekimab in patients with moderate to severe atopic dermatitis. The study is multicenter, and will consist of two dose levels: Bermekimab administered subcutaneously at a dose of 200 mg weekly (4 doses) and bermekimab administered subcutaneously at a dose of 400 mg weekly (8 doses). Patients taking the 200mg dose will be followed for 5 weeks (6 visits, day 35 ± 20 , and patients taking the 400mg dose will be followed for 8 weeks (9 visits, day 56 ± 20) to allow for assessment of safety and preliminary efficacy.

Dose escalation details can be found in Section 5.3.

The protocol of the study will be approved by the Institutional Review Board (IRB) or the Ethics Committee (EC) of the participating study sites. Depending on the participating countries, both local and central IRB/EC approvals will be granted. The study will be registered at www.clinicaltrials.gov before the enrollment of the first patient. The trial will be conducted in compliance with the protocol, GCP, and all applicable regulatory requirements.

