refrigeration and lay flat; allow to warm to room temperature. Do not heat

Pre-injection

- Concomitant medications/treatments
- o DLQI
- Urine pregnancy
- o EASI
- o IGA
- HADS
- Pruritus/Pain NRS: data from patient diary to be recorded at this time if available
- o SCORAD
- o POEM
- o GISS
- Vital signs (blood pressure, pulse, oxygen saturation, respiratory rate and body temperature)

Bermekimab subcutaneous injection in accordance with injection site determined by BMI at Screening

Post bermekimab subcutaneous injection

- 1 hour monitoring post-injection
 - Injection reaction
 - Vital signs (blood pressure, pulse, oxygen saturation, respiratory rate and body temperature) one hour post injection (70 +/- 10 minutes)
- Adverse event monitoring

Visit 8 (day 49 +/- 2)

> *At least 45 minutes before injection*: When using pre-filled syringes, remove syringe from

refrigeration and lay flat; allow to warm to room temperature. Do not heat

Pre-injection

- Concomitant medications/treatments
- Urinalysis
- Electrocardiogram (ECG) (patient should be supine for at least 5 minutes prior to performating ECG)
- Physical Examination
- o DLQI
- Urine pregnancy
- o EASI
- o IGA
- o HADS
- Pruritus/Pain NRS: data from patient diary to be recorded at this time if available
- o SCORAD
- o POEM
- o GISS
- Blood draw:
 - chemistry and hematology, 12.5mL
 - PK and Biomarker Analysis, 6mL
- Vital signs (blood pressure, pulse, oxygen saturation, respiratory rate and body temperature)

Bermekimab subcutaneous injection in accordance with injection site determined by BMI at Screening

Post bermekimab subcutaneous injection

- ➤ 1 hour monitoring post-injection
 - Injection reaction
 - Vital signs (blood pressure, pulse, oxygen saturation, respiratory rate and body temperature) one hour post injection (70 +/- 10 minutes)
- Adverse event monitoring

Visit 9 (56 +/- 2)

- Concomitant medications/treatments
- > DLQI
- Physical Examination
- ► EASI
- ► IGA
- > HADS
- > Pruritus/Pain NRS: patient diary to be retained and data to be recorded
- > SCORAD
- > POEM
- ➢ GISS
- Vital signs (blood pressure, pulse, oxygen saturation, respiratory rate and body temperature)
- Adverse Event Monitoring

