5.2 STUDY CALENDAR

Visit	Screen	1	2	3	4	5	6	7	8	9
Study Day		0	7 ±2	14 ± 2	21 ±2	28 ± 2	35 ± 2	42 ± 2	49 ± 2	56 ± 2
Informed Consent	Х									
Demography, Height, Weight ^f	х									
Medical History	х									
Infectious Disease Panel +	Х									
IGRA ^e	х									
Serum Pregnancy	Х									
Physical Examination	Х					Х			Х	Х
Urinalysis ▲		Х			Х				х	
Electrocardiogram (ECG)£		Х							Х	
Visit 1 Questionnaire ◆		Х								
Vital Signs ⁺	Х	Х	Х	Х	Х	Х	Х	Х	Х	Х
Urine Pregnancy		Х	х	Х	Х	х	Х	Х	х	
Blood Draw	x ^{ab}	x ^c		xabc		xabc			xabc	
Bermekimab Injection �		Х	Х	Х	Х	Х	Х	Х	Х	
EASI	Х	Х	х	х	Х	х	х	х	х	х
IGA	Х	Х	Х	Х	Х	Х	Х	Х	Х	Х
SCORAD	Х	Х	х	Х	Х	х	Х	Х	Х	Х
DLQI		Х	х	х	Х	х	х	х	х	х
Pruritus/pain NRS ^d		Х	Х	Х	Х	Х	Х	Х	Х	Х
POEM		Х	х	Х	Х	х	Х	Х	х	х
GISS		Х	Х	Х	Х	Х	Х	Х	Х	Х
HADS		X	х	X	Х	X	X	X	X	X
Adverse Events		Х	х	Х	Х	X	Х	Х	Х	х
Concomitant	X	X	х	х	X	х	X	X	Х	х
Meds/Treatments*										

^a Chemistry Panel including: Albumin, Alkaline Phosphatase, ALT, AST, GGT, Bicarbonate (CO2) Calcium,

Chloride, Creatinine, Glucose, Potassium, Sodium, Total Bilirubin, Total Protein, Urea Nitrogen

^b Hematology Panel including: Complete whole blood (WBC, HgB, Platelet, differential)

^cBlood draw for PK and Biomarker analysis

^d Data from patient diary for the previous 7 days to be recorded at this time.

^e Interferon gamma release assay

^fBMI will be calculated at this visit using height and weight

+HIV antibody, Hepatitis C antibody, Hepatitis B panel (HBsAg, anti-HBc, anti-HBs), and interferon gamma release assay (IGRA)

▲ Urinalysis will assess pH, protein, glucose, and blood cells

 \pounds A standard 12-lead ECG will be performed. The ECG strips and/ or reports will be retained with the source documentation.

✤ Each bermekimab injection will be followed by 1 hour monitoring for injection site reaction and vital signs 1 hour post injection (70+/- 10 minutes)

⁺ Vital signs include blood pressure, pulse, oxygen saturation, respiratory rate and body temperature

✦ Assessment of patients Pruritus, Pain and Erythema will be recorded twice [once pre-injection, once post-injection of bermekimab] during visit 1.

* Concomitant medications within 30 days before screening until 7 days after the last administration of the study drug must be recorded for the purpose of drug-drug and drug-disease interaction evaluation and signal detection.

BMI: Body Mass Index [BMI= weight (kg)/height (m²)]
IGRA: Interferon Gamma Release Assay
DLQI: Dermatology Life Quality Index

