The SCORAD is a validated tool used in clinical research and clinical practice that was developed to standardize the evaluation of the extent and severity of AD. There are 3 components to the assessment: A = extent or affected body surface area, B = intensity, and C = subjective symptoms. The extent of AD is assessed as a percentage of each defined body area and reported as the sum of all areas, with a maximum score of 100% (assigned as "A" in the overall SCORAD calculation). The intensity of 6 specific symptoms of AD (redness, swelling, oozing/crusting, excoriation, skin thickening/ lichenification, dryness) is assessed using the following scale: none (0), mild (1), moderate (2), or severe (3) (for a maximum of 18 total points, assigned as "B" in the overall SCORAD calculation). Subjective assessment of itch and sleeplessness is recorded for each symptom by the patient or relative on a VAS, where 0 is no itch (or sleeplessness) and 10 is the worst imaginable itch (or sleeplessness), with a maximum possible score of 20. This parameter is assigned as "C" in the overall SCORAD calculation. The SCORAD is calculated as: A/5 + 7B/2 + C where the maximum is 103.

Patient Assessment of Pruritus and Pain

The NRS is a simple assessment tool that patients will use to report the intensity of their pruritus (itch) and pain during a daily recall period using a study diary. Patients will be asked to complete the following questions:

- For average itch intensity: "On a scale of 0 to 10, with 0 being 'no itch' and 10 being the 'worst itch imaginable', how would you rate your itch **on average** during the previous 24 hours?"
- For maximum itch intensity: "On a scale of 0 to 10, with 0 being 'no itch' and 10 being the 'worst itch imaginable', how would you rate your itch at the **worst moment** during the previous 24 hours?"
- For pain intensity: "On a scale of 0 to 10, with 0 being 'no pain' and 10 being the 'most severe pain', how would you rate your pain **on average** during the previous 24 hours?"

Patients will be instructed to record their NRS score daily from day 0 to day 56 (+/-2). Sites will be expected to review the diary at each visit and enter the data from the previous 7 days.

Visit 1 Questionnaire for Pruritus, Pain and Erythema

The following questions assess the intensity of pruritus (itch) and pain experienced by the patient before and after the injection of bermekimab during visit 1. The patient will answer the following questions:

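### Section 3 ends Group A's follow-up at visit 6, but the efficacy endpoints, per-protocol entry and the only post-dose ECG are set at visit 8

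*Combined protocol and SAP*

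**What the plan says.** **Group A's regimen.** The synopsis gives Group A four 200 mg injections: "Dosing will occur weekly from visit 1 to visit 4". Section 3 agrees: "Bermekimab administered subcutaneously at a dose of 200 mg weekly (4 doses".

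**Group A's follow-up.** Section 3 is the only place that states it for this group: "Patients taking the 200mg dose will be followed for 5 weeks (6 visits", ending at day 35. The diary issued at screening (Section 5.1) covers days 0 to 35, which fits, although that text names no group.

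**Text that runs longer without separating the groups.** The synopsis describes participation as "including a 2 week screening period, a 7 week treatment period, and 1 week follow up period". Section 2.9 treats visit 9 as the end of study: any treatment "administered from the time of consent to the end-of-study visit (visit 9) is considered concomitant". Section 8.2 says "Patients will be instructed to record their NRS score daily from day 0 to day 56". Section 9.3 records adverse events to visit 9.

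**What is set at visit 8.** In Section 3.1 the change scores and responder rates are taken at visit 8, and a missing visit 8 IGA counts as non-response. Section 10.3.1 admits to the per-protocol set only patients assessed at both baseline and visit 8. Section 10.5.4 summarises visit 8 change and response by group and pooled. The Section 5.2 calendar has ECGs at visits 1 and 8 only.

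**The injection schedule.** Section 5.1 repeats "Bermekimab subcutaneous injection in accordance with injection site determined by BMI at Screening" at every visit from 1 to 8. The calendar marks all eight visits, and the footnote to that row sets no group limit: "Each bermekimab injection will be followed by 1 hour monitoring for injection site reaction and vital signs 1 hour post injection".

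**The concern.** The visit schedule and endpoint definitions fit Group B, the cohort that attends nine visits. Section 3 gives Group A a shorter follow-up, and the endpoint, analysis-set and calendar text was not adapted to it.

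Three things are at stake. First, the plan would report a zero IGA response at 200 mg that comes from the calendar and says nothing about the drug. The study is meant to range doses as a basis for randomized trials (Section 1.2), so that figure could mislead. Second, the pooled summaries would either carry that zero or, in the per-protocol set, contain Group B alone. Third, safety is the primary endpoint. Section 7 names ECG as a safety measure and Section 10.6.2 summarises it by group, yet Group A would have only a pre-dose tracing.

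The unlabelled injections at visits 5 to 8 are a separate and lesser matter. A site working visit by visit from Section 5 finds an injection instruction at visits 5 and 6, where Group A should receive none.

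**Working it through.** The plan gives no calculation to reproduce on this point, since Section 10.2 calls the sample size one of convenience. The check is a count of scheduled events.

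**Inputs.** Group sizes 9 and 20, total 29 (synopsis). Group A doses on days 0, 7, 14 and 21; visits 5, 6 and 8 on nominal days 28, 35 and 49 (Section 5.2). Group A attends visits 1 to 6 (Section 3).

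**Step 1: what falls within visits 1 to 6** (after screening).

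| Assessment | Calendar visits | Available to Group A |
|---|---|---|
| ECG | 1, 8 | 1 (pre-dose), so none after any dose |
| Urinalysis | 1, 4, 8 | 1 and 4 (visit 4 precedes dose 4), so none after dose 4 |
| PK sample | 1, 3, 5, 8 | 3 of 4 |
| Chemistry and hematology | 3, 5, 8 | 3 and 5 |
| Physical examination | 5, 8, 9 | 5 |
| Vital signs, adverse events | all | all six |
| Visit 8 efficacy scores | 8 | none |

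**Step 2: IGA response (0 or 1).** With no visit 8 score, Group A is 0 of 9 by rule. The pooled rate is at most (0 + 20)/29 = 69.0%, so any Group B rate is multiplied by 20/29. As an illustration only, if 10 of 20 in Group B responded (50%), the pooled figure would be 10/29 = 34.5%. The 95% interval that Section 10.5.4 asks for would have no sampling meaning around a zero imposed by rule.

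**Step 3: per-protocol set.** Group A contributes 0 of 9. The pooled set is at most 20/29 = 69.0% of patients, all from Group B.

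**Step 4: change scores.** Group A has no visit 8 value, so there is nothing to summarise for it in either analysis set.

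**Step 5: candidate Group A visits.** Visit 5 is 28 - 21 = 7 days after Group A's last dose. That matches Group B's pre-injection visit 8, which is 49 - 42 = 7 days after its seventh dose. Visit 6 is 35 - 21 = 14 days after Group A's last dose. At visit 5, before any injection, both groups have had four doses.

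**Step 6: the injection label.** By design, Group A receives 4 x 200 = 800 mg. Read literally, Section 5 gives 6 x 200 = 1200 mg by visit 6, or 8 x 200 = 1600 mg by visit 8. Group B's planned total is 8 x 400 = 3200 mg.

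**The case against.** **The dose is not in doubt.** The synopsis and Section 3 agree on four doses, and Section 5 can be read as one list written for the longer cohort. This stands. A reader might infer from the schedule that Group A would receive 1600 mg. The documents do not support that: it is a literal-reading ceiling, half of Group B's planned total. Dispensing logs (Section 11.9), monitoring of protocol adherence (Section 11.11) and the dose-count summary (Section 10.7.1) would help expose an error. The missing label is a wording correction with limited chance of harm.

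**Group A may in fact attend to visit 8 or 9.** Several sections run that far. None separates the groups, however, while Section 3 speaks of Group A specifically and the screening diary fits it. The consequences follow from Section 3 as written; that Group A will miss visit 8 is not established beyond doubt. If it does attend, the endpoints stand and it has one post-dose ECG, 49 - 21 = 28 days after its last dose.

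**The stakes are limited.** Safety is primary, no formal test is planned for it, the dose groups are not compared, and the secondary endpoints are also analysed in the safety set. All true, but using the safety set does not help: it retains the 9 patients without giving them visit 8 data, and the IGA rule then scores them as failures. Descriptive results still need an endpoint that the group can reach.

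**Group A might seem unmonitored for safety.** It is not. Laboratory tests at visits 3 and 5, an examination at visit 5, and vital signs and adverse events throughout all remain. The PK loss is small, since the visit 5 sample already follows dose 4.

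**Conclusion.** The point holds and should be fixed. If Section 3 governs Group A's attendance, the plan gives 0 of 9 IGA responders by rule, a pooled rate capped at 69.0%, no Group A patient in the per-protocol set, no Group A visit 8 change score and no scheduled Group A ECG after dosing. These results rest on one assumption, that Group A's last visit is visit 6. Section 3 says so and the screening diary supports it, but sections that do not separate the groups leave it open.

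A zero for Group A produced this way should not be read as evidence that 200 mg is ineffective. The unlabelled injections are secondary and would not merit much weight alone. Labelling them would leave the visit 8 problem untouched.

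**What to change.** **If Group A ends at visit 6:**

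- In Sections 5.1 and 5.2, mark the injections at visits 5 to 8 as Group B only. For Group A, show visits 5 and 6 as follow-up without injection and visits 7 to 9 as not applicable.
- Move Group A's visit 8 ECG and urinalysis to visit 6.
- In Sections 3.1, 10.3.1 and 10.5.4, replace visit 8 for Group A with one named visit, covering the endpoints, the IGA missing-data rule and per-protocol entry. Visit 5 matches Group B's gap since last dose; visit 6 is Group A's last visit. Either is defensible if fixed in advance.
- Report pooled efficacy only at a shared visit, for example visit 5 after four doses in each group, or give visit 8 results by group only. Otherwise, with visit 5 named for Group A, the pooled summaries would mix day 28 after four doses with day 49 after seven.
- Align the synopsis and Sections 2.9, 8.2 and 9.3 with the group-specific last visit.

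**If Group A is meant to attend visit 8 or 9:** correct the five weeks and six visits in Section 3, keep the visit 8 endpoints, and still label the injections. The diary period in Section 5.1 then needs extending too.

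**Cost.** A protocol amendment through the full approval procedure (Section 11.3), one re-timed ECG and urinalysis at a visit that 9 patients already attend, and efficacy timepoints that differ by group.

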5.2 STUDY CALENDAR

Visit	Screen	1	2	3	4	5	6	7	8	9
Study Day		0	7 ±2	14 ± 2	21 ±2	28 ± 2	35 ± 2	42 ± 2	49 ± 2	56 ± 2
Informed Consent	Х									
Demography, Height, Weight ^f	х									
Medical History	х									
Infectious Disease Panel +	Х									
IGRA ^e	х									
Serum Pregnancy	Х									
Physical Examination	Х					Х			Х	Х
Urinalysis ▲		Х			Х				х	
Electrocardiogram (ECG)£		Х							Х	
Visit 1 Questionnaire ◆		Х								
Vital Signs ⁺	Х	Х	Х	Х	Х	Х	Х	Х	Х	Х
Urine Pregnancy		Х	х	Х	Х	х	Х	Х	х	
Blood Draw	x ^{ab}	x ^c		xabc		xabc			xabc	
Bermekimab Injection �		Х	Х	Х	Х	Х	Х	Х	Х	
EASI	Х	Х	х	х	Х	х	х	х	х	х
IGA	Х	Х	Х	Х	Х	Х	Х	Х	Х	Х
SCORAD	Х	Х	х	Х	Х	х	Х	Х	Х	Х
DLQI		Х	х	х	Х	х	х	х	х	х
Pruritus/pain NRS ^d		Х	Х	Х	Х	Х	Х	Х	Х	Х
POEM		Х	х	Х	Х	х	Х	Х	х	х
GISS		Х	Х	Х	Х	Х	Х	Х	Х	Х
HADS		X	х	X	Х	X	X	X	X	X
Adverse Events		Х	х	Х	Х	X	Х	Х	Х	х
Concomitant	X	X	х	х	X	х	X	X	Х	х
Meds/Treatments*										

^a Chemistry Panel including: Albumin, Alkaline Phosphatase, ALT, AST, GGT, Bicarbonate (CO2) Calcium,

Chloride, Creatinine, Glucose, Potassium, Sodium, Total Bilirubin, Total Protein, Urea Nitrogen

^b Hematology Panel including: Complete whole blood (WBC, HgB, Platelet, differential)

^cBlood draw for PK and Biomarker analysis

^d Data from patient diary for the previous 7 days to be recorded at this time.

^e Interferon gamma release assay

^fBMI will be calculated at this visit using height and weight

+HIV antibody, Hepatitis C antibody, Hepatitis B panel (HBsAg, anti-HBc, anti-HBs), and interferon gamma release assay (IGRA)

▲ Urinalysis will assess pH, protein, glucose, and blood cells

 \pounds A standard 12-lead ECG will be performed. The ECG strips and/ or reports will be retained with the source documentation.

✤ Each bermekimab injection will be followed by 1 hour monitoring for injection site reaction and vital signs 1 hour post injection (70+/- 10 minutes)

⁺ Vital signs include blood pressure, pulse, oxygen saturation, respiratory rate and body temperature

✦ Assessment of patients Pruritus, Pain and Erythema will be recorded twice [once pre-injection, once post-injection of bermekimab] during visit 1.

* Concomitant medications within 30 days before screening until 7 days after the last administration of the study drug must be recorded for the purpose of drug-drug and drug-disease interaction evaluation and signal detection.

BMI: Body Mass Index [BMI= weight (kg)/height (m²)]
IGRA: Interferon Gamma Release Assay
DLQI: Dermatology Life Quality Index
EASI: Eczema Area and Severity Index Score
IGA: Investigator's Global Assessment
NRS: Numerical Rating Scores
SCORAD: Severity Scoring of Atopic Dermatitis
POEM: Patient Oriented Eczema Measure
GISS: Global Individual Signs Score
HADS: Hospital Anxiety Depression Scale

